Mirtazapine has potent anti-emetic properties and is available as an oral disintegrating formulation. It is used off-label to treat nausea and vomiting during cancer chemotherapy,¹ prevent post-surgical nausea and vomiting ² and for gastroparesis.³ It is marketed as the serotonin-norepinephrine reuptake inhibitor antidepressant Remeron[®]. Mirtazapine has multiple receptor effects beyond those involved in reducing depressive symptoms. It produces rapid resolution of nausea and vomiting by blocking physiologic inputs that coordinate emesis (Figure 1).

Mirtazapine is available as RemeronSolTab[®] (oral dissolvable) and tablet forms, which will be prescribed for the 3-week trial, and Remeron[®] tablets will be prescribed for the continuation phase. The acquisition and dispensing of the drugs will be under the organizational SOP for the Research Pharmacy at Northwestern Medicine.

An IND will be submitted along with the approved consent form following this review. The IND submission is included in the documents section of this application. The sponsor is the PI, [name].

PROCEDURES INVOLVED

Enrollment. The participant will provide demographic data (age, self-identified race and ethnicity), height and weight. All prescription, over-the-counter medications, alcohol and other drugs taken by the subject in the week prior to study entry and during labor and delivery will be recorded.

Blood pressure, heart rate, fetal heart rate, complete blood count, comprehensive metabolic screen (includes electrolytes and liver function studies) and urinalysis will be collected for assessment of sNVP. Any electrolyte abnormality will be corrected before the administration of mirtazapine. An ECG will be performed in all subjects at baseline, at the end of the initial three weeks, and monthly in subjects who continue mirtazapine beyond the three-week study. The ECG will be done to evaluate the emergence of QT prolongation, Torsades de Pointes, ventricular tachycardia, or other abnormal cardiac findings. Although maximum QTc interval, Tp-e interval and Tp-e/QT ratio are increased in the late pregnancy, they all remain within the normal ranges.⁴²

Figure 2. PUQE Scoring System							
Not at all (1)	1 hour or less (2)	2-3 hours (3)	4-6 hours (4)	More than 6 hours (5)			
7 or more times (5)	5-6 times (4)	3-4 times (3)	1-2 times (2)	l did not throw up (1)			
No time (1)	1-2 times (2)	3-4 times (3)	5-6 times (4)	7 or more times (5)			

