Med Log \rightarrow	\rightarrow	\rightarrow	\rightarrow	\rightarrow	\rightarrow	\rightarrow	\rightarrow	\rightarrow	\rightarrow	\rightarrow	\rightarrow	\rightarrow	\rightarrow	\rightarrow	\rightarrow	\rightarrow	\rightarrow	\rightarrow	\rightarrow	\rightarrow		

Trial Protocol Overview (Figure 3).

Acceptability. The participant's medical status and drug treatment for sNVP will be reviewed by the study obstetrician. As in clinical practice, other anti-emetic drugs may be continued if desired by the participant and recommended by the obstetrician. The subject's decision to accept or decline will be recorded and she will be asked to provide the reason(s) for her decision. Pregnant persons who enroll will be given mirtazapine to begin treatment that evening or at a time recommended by the obstetrician. Intervention for pregnant persons who decline to participate will be coordinated by their obstetrical care professional.

Mirtazapine Regimen. The dose of mirtazapine for depression (15-45 mg/day) may not be the same as for achieving its antiemetic effect because the targeted receptors differ. We will begin with 15 mg, which is the lowest dose of the oral disintegrating tablet available. A telephone or telehealth follow-up for side effects will be conducted on day 2. Dose increases will occur weekly during the visits as depicted in Figure 3 unless the patient has prohibitive side effects or remission of sNVP. Remission is defined as a PUQE score of 3 (no symptoms) or 4 (1 hour or less of nausea without retching or vomiting). Side effects assessment will occur the day after each dose increase to evaluate tolerability. Reduction to the previous dose will occur if side effects are burdensome. Although the modal dose of mirtazapine from case reports is 30 mg. tolerability studies in persons with NVP have not been published. Steady-state plasma concentrations of mirtazapine occur within 5 days³² and will be achieved across the week prior to dose escalations. Weekly plasma concentrations will be obtained to confirm absorption of mirtazapine and explore associations with side effects. Sampling will occur at a consistent time of day for each woman; ideally, the time will be in the late afternoon during the drug elimination phase as close to the trough concentration as feasible. Adverse events will be reviewed by the DSMB after every 5 subjects to determine whether a protocol or dosing change is warranted.

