Side Effect Assessment, Before mirtazapine treatment, a comprehensive metabolic profile and urinalysis will be obtained as standard of care. An ECG also will be performed. The degree of QT prolongation observed with both 45 mg (therapeutic) and 75 mg (supra-therapeutic) doses of mirtazapine was not clinically meaningful,⁴⁷ and QTc ≥500 msec was not observed among mirtazapine-treated patients.⁵⁰ The drug regimen to which mirtazapine may be added will be reviewed by [name], a fellowship-trained clinical pharmacologist and obstetrician, for QTc prolongation risk prior to mirtazapine administration, or [name], an attending obstetriciangynecologist in Obstetrical Triage, or [name], the PI, a perinatal psychopharmacologist. Side effects will be assessed with the 14-item Asberg Side Effects (ASE)⁵¹ scale, which was adapted by our team for SSRI-treated pregnant persons.^{52,53} The ASE guantifies discomforts from mild to severe and a summary of overall distress. Serotonin hyper-stimulation will be reviewed with Hunter's Decision Rules for Diagnosis of Serotonin Toxicity (SS).⁵⁴ SS is characterized by tachycardia, diaphoresis, myoclonus and tremor.⁵⁵ The incidence of SS is infrequent (9/10,000) as shown in a retrospective cohort study⁵⁶; however, ondansetron, metoclopramide and mirtazapine have been associated with SS during monotherapy and with other serotonergic drugs⁵⁷, although rarely in young persons.⁵⁸ Treatment includes drug discontinuation, benzodiazepines and the anti-serotonergic drug cyproheptadine.

Specific Instrument Use

Pregnancy Unique Quality of Emesis (PUQE)⁴³ **scale (Figure 2):** We will utilize the PUQE scale to capture the severity of nausea and vomiting in pregnancy based on three physical symptoms: nausea, vomiting, and retching over the previous 24 hours. A PUQE score of < 6 is considered mild, a score from 7-12 is moderate, and a score of 13+ is considered severe. This scale will be entered daily in REDCap directly by the participant.

Self-Administered Comorbidity Questionnaire (SCQ)⁵⁹**:** The Comorbidity Questionnaire (CQ) assesses comorbid conditions in clinical and health services research. The questionnaire is self-administered, short, easily understood, and can be completed by individuals without any medical background. It also allows the subject to note the severity of each comorbid conditions and their perception of its impact on their function.

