PROMIS Global Health⁶³: The PROMIS Global Health item scale assesses overall health. The global health items include ratings of the five primary PROMIS domains (physical function, fatigue, pain, emotional distress, social health) as well as perceptions of general health that cut across domains. Global items allow respondents to weigh together different aspects of health to arrive at a "bottom-line" indicator of their health. Similar global health items have been found predictive of future health care utilization and mortality. The PROMIS Global Health items include the most widely used single self-rated health item ("In general, would you say your health is . . ."). Previous research has shown that this item taps physical and mental health about equally but reflects physical health more than mental health among respondents at lower income levels. PROMIS Global Health items include specific ratings of physical health and mental health, as well as a rating of overall quality of life. The remaining items provide global ratings of physical function, fatigue, pain, emotional distress, and social health. The PROMIS Global Health items can be administered as individual items or combined to produce separate physical and mental health summary scores.

Columbia-Suicide Severity Rating Scale (C-SSRS)⁷⁷: The Columbia-Suicide Severity Rating Scale (C-SSRS) is a questionnaire used for suicide assessment that was developed with NIMH support. The scale is evidence-supported and is part of a national and international public health initiative involving the assessment of suicidality. Suicidal ideation will be assessed at baseline, during, and 28 days after treatment cessation if there were any abnormalities during the trial.

DATA AND SPECIMEN BANKING

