An individual subject will stop participating in the clinical trial in the instance of any of the following:

- New onset suicidal thoughts or behaviors
- Grade 3 or higher drug-related serious adverse event (SAE) based on the CTCAE, version 5.0
- Acute livery injury [alanine transaminase (ALT) or aspartate transaminase (AST) > 3-fold upper limit of normal (ULN), alkaline phosphatase (ALP) or total bilirubin (TBL) > 2 fold ULN]
- Subjects with serum sodium < 125 mmol/L

PROTECTED HEALTH INFORMATION (PHI AND HIPAA)

This study involves the creation, use or disclosure of Protected Personal Health Information. Protected Personal Health Information includes names, address, dates of birth and ages, telephone numbers, email addresses, social security numbers (see Compensation section), and medical record numbers. HIPAA requirements and measures to protect PHI will be implemented as described in the Data Management and Confidentiality section.

QUALIFICATIONS TO CONDUCT RESEARCH AND RESOURCES AVAILABLE

An interdisciplinary team with a strong commitment to improving care for pregnant persons collaborated in the development of this protocol. Northwestern is the sole clinical site for this study. The PI is [name], MS, is the Norman and Helen Asher Professor of Psychiatry and Obstetrics and Gynecology. She has conducted nine NIMH-funded R01 observational (during pregnancy) and randomized clinical trial (postpartum) studies of mood disorders. [name] was an author in the joint ACOG-APA Committee's consensus report for managing depression during pregnancy ⁷⁶ and is the first author of *Mental Health and* Behavioral Disorders, in Obstetrics: Normal and Problem Pregnancies, edited by Gabbe S et al (2007, 2012) and Psychotropic Drugs (in Schaefer C et al, Drugs during Pregnancy and Lactation: Treatment Options and Risk Assessment, 2014). She is a fellow of the American College of Neuropsychopharmacology. [name] participated in the FDA Advisory Committee to Revise Drug Labeling for Pregnancy and Lactation; FDA Pediatrics Subcommittee, Neonatal Effects of SSRI Use; Research Committee, Organization of Teratology Information Services; FDA Advisory: Perinatal Depression-Examining the Risks and Benefits of Treatment; CDC TRxeating for Two: Safe Medication Use in Pregnancy Expert Meeting. Drs. [name] and [name] (see below) are Co-PIs on the Northwestern Obstetric-Fetal Pharmacology Research Center funded by NICHD.

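### Once dosing begins, the liver-test and sodium stops for individual participants have no scheduled blood chemistry behind them

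*Protocol*

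**What the plan says.** The protocol's Trial Stopping Criteria take an individual out of the trial on two laboratory findings. The liver rule begins "alanine transaminase (ALT) or aspartate transaminase (AST) > 3-fold upper limit of normal (ULN") and goes on to ALP or total bilirubin above twice ULN. The sodium rule reads "Subjects with serum sodium < 125 mmol/L". Neither requires the abnormality to be drug-related.

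Chemistry that would supply these values appears in two places, both before dosing. Under Procedures Involved, the Enrollment paragraph says that a "comprehensive metabolic screen (includes electrolytes and liver function studies) and urinalysis will be collected for assessment of sNVP" and adds: "Any electrolyte abnormality will be corrected before the administration of mirtazapine". The Side Effect Assessment paragraph says: "Before mirtazapine treatment, a comprehensive metabolic profile and urinalysis will be obtained as standard of care".

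Other safety checks have stated repeats. For cardiac safety: "An ECG will be performed in all subjects at baseline, at the end of the initial three weeks, and monthly in subjects who continue" beyond week 3. For the C-SSRS: "Suicidal ideation will be assessed at baseline, during, and 28 days after treatment cessation", the last of these only if something abnormal was seen during the trial.

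The Mirtazapine Regimen paragraph makes escalation the default: "Dose increases will occur weekly during the visits as depicted in Figure 3 unless the patient has prohibitive side effects or remission of sNVP".

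**The concern.** A mandatory stop works only if someone measures the quantity that triggers it. Side-effect scales, weight and blood pressure do not measure sodium or transaminases. If the protocol schedules no chemistry on treatment, whether a participant is stopped depends on whether her clinicians ordered a test as well as on her laboratory value. Two participants with the same value could be handled differently, and one of them would go on to higher doses.

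Safety is part of the primary objective and of Aim 2. The sponsor plainly regards electrolytes as relevant, because abnormalities must be corrected before the first dose. Patients with hyperemesis gravidarum are eligible (Figure 6), and the Objectives section lists electrolyte disturbance among the features of that condition. The same is not claimed for every entrant with severe nausea and vomiting. The primary outcome and the SAP analyses are not affected.

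**Working it through.** The plan gives no figure to reproduce here. The check sets the stated tests against the rules that need them, then measures the time without a test and counts the panels a fix would need.

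**1. Rules against stated tests**

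| Safety item | Measurement needed | Before dosing | On treatment |
|---|---|---|---|
| Liver stop | ALT, AST, ALP, total bilirubin | One panel | None stated |
| Sodium stop | Serum sodium | Same panel | None stated |
| Suicidality stop | C-SSRS | Yes | Yes |
| Cardiac monitoring | ECG | Yes | End of week 3, then monthly |

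The pre-treatment panel could itself meet the stopping wording, so the rules are not empty. The gap is confined to the time after the first dose. The weekly blood draws have a different stated purpose: to confirm absorption and explore links with side effects.

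Figures 3 and 4 list no chemistry, and Risks to Participants assigns the follow-up blood to drug concentration. I do not rely on these. Figure 3 and the blood volumes also omit the baseline panel, and Figure 4 omits the monthly ECG that the text requires. The conclusion rests on the two prose descriptions of the panel, both pre-treatment, and on finding no repeat elsewhere in either document.

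**2. What following the text produces**

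Take two participants, each with sodium below 125 mmol/L at day 7, without prohibitive side effects and not in remission. If one has chemistry ordered in clinical care, she stops. If the other has none ordered, the regimen takes her to 30 mg on day 8 and 45 mg on day 15.

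**3. Time on drug without a stated check**

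- Three-week trial, full escalation (Figure 3): days 1-7 at 15 mg, days 8-14 at 30 mg, days 15-21 at 45 mg. Days above the starting dose: 7 + 7 = 14, and 14/21 = 67%.
- Longest continuation case: entry at 5 weeks' gestation (the example in the Compensation section), treated to delivery. Delivery week is my assumption: 37 − 5 = 32 weeks, or 40 − 5 = 35 weeks.
- For comparison, the seven-case series in the Background section had a mean treatment duration of 9.1 weeks (range 4-24).

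**4. Panels needed**

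Three-week trial, three draws each: 25 × 3 = 75 as planned; 20 × 3 = 60 for the 20 expected completers; 2 × 3 = 6 for the 2 actually enrolled.

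Continuation, per participant in the longest case. The Compensation section allows several readings of the visit schedule and its maximum of 10:

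- 4-weekly from week 3, no cap: (32 − 3)/4 = 7.25, so 7; (35 − 3)/4 = 8.
- Cap on all post-intake visits, 4-weekly continuation: 10 − 3 = 7 (6 if intake counts).
- Same cap, with the five additional weeks as weekly visits: 10 − 3 − 5 = 2 monthly visits (1 if intake counts).
- Monthly only after week 8, cap on monthly visits only: (32 − 8)/4 = 6; (35 − 8)/4 = 6.75, so 6.

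The range is 1 to 8. Later entry or a shorter course would lower the number.

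**The case against.** The strongest reply is that silence is weak evidence here. The figures and blood volumes are visibly incomplete, the baseline panel is called standard of care, and on-treatment chemistry may have been left to clinical practice. The manual of operating procedures and the IND submission were not supplied, and either could hold a laboratory schedule. That possibility stands. But the stops themselves and the ECG timing are in the protocol, so the chemistry timing belongs there too. If a schedule exists elsewhere, one sentence closes the point.

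Second, there are safeguards: weekly visits, a side-effect check the day after each increase, DSMB review of emergency visits and hospitalizations, the obstetrician's power to discontinue, and the team's duty to respond to a worsening condition such as severe dehydration. These make it likely that a symptomatic event would be found. They work through clinical recognition, however, and none schedules a blood test. The gap that remains is the participant with a qualifying value, no prohibitive symptom and no clinical test. The documents do not say how often that would occur, and do not state that mirtazapine causes either abnormality.

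Third, asking for weekly panels may look like preference, since the ECG is itself repeated only at the end of week 3. A day 21 panel would be better than none, but it comes after both increases and could inform neither.

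Fourth, doses rise at the visit, so a same-day result may come too late. That is a fair practical point. Prompt review would still limit time at the higher dose to the laboratory turnaround.

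**Conclusion.** The concern holds as a statement about the supplied text. Two mandatory individual stops rest on blood chemistry, and no chemistry is stated after dosing begins. The rules are not inoperable, but on treatment they would be applied unsystematically. The exposure is 21 days for a completer who escalates fully, 14 of them above 15 mg, and at most 32 to 35 weeks in continuation, assuming entry at 5 weeks' gestation and delivery at 37 to 40 weeks. These figures measure unchecked time. The documents give no event rate for either stop and no frequency of clinical testing, so risk cannot be estimated. This should be fixed: it is a safety-ascertainment gap that is cheap to close. The SAP records closure after 2 participants, both of whom completed the three weeks, so the practical use is in a reopened or follow-on protocol.

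**What to change.** Add a metabolic panel (sodium, ALT, AST, ALP, total bilirubin) to the existing draws on days 7, 14 and 21 and to each 4-weekly continuation draw. Review the day 7 and day 14 results before the increases to 30 and 45 mg or promptly after them, and stop the participant if a threshold is met. State in Trial Stopping Criteria that results from clinical testing between visits also count. List the panel under Procedures Involved and in Figures 3 and 4.

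The cost is a protocol amendment plus one extra tube and a laboratory fee per draw, with no added visit or venepuncture: 75 panels for the planned 25 participants in the three-week trial, and 1 to 8 more per participant in the longest continuation case. Waiting for a result before escalating may delay an increase.

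The main downside is more stops. Neither individual criterion requires drug-relatedness, and neither does the whole-trial bullet on Grade 3 or higher toxicity in any organ system. Closer testing in a condition that can itself disturb electrolytes could therefore trigger both levels more often. The sponsor should decide in advance whether values attributable to the disease count towards the whole-trial stop.

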- 4. Establish a manual of operating procedures (MOP) to ensure regulatory compliance, policy development, record-keeping practices, coordinated oversight of recruitment, management of subject data and human subject issues. The MOP will include information on all aspects of the study, such as organizational structure, screening, inclusion/exclusion criteria; treatments, collection, shipping and location of specimens, adverse events, data entry and management, statistical analysis and publications. Protocol updates and clarifications from study meetings will be included in the dynamic MOP, which will be updated weekly during the investigation. The final version of the MOP will contain all information need to construct the later definitive clinical trial to be submitted as an R01 if the data from this study are supportive.
- 5. A decision-making algorithm for data reporting procedures will be developed and placed in the MOP. Quality assurance procedures, such as frequent data quality reviews and direct observation of research staff conducting procedures, will be devised. Training and ongoing supervision of research staff are essential to promoting intervention fidelity. We will develop (and modify iteratively) training procedures and scripts for interacting with participants at each visit. Training will include review of the MOP, data collection and management systems, and quality control procedures. Staff will have hands-on experience with the data system by entering mock data and reviewing reporting procedures.
- 6. The data team will generate reports for the review of the study team (with attention to sections that must be kept blind by the clinical team), as well as for DSMB and FDA review. Criteria will include enrollment of participants, frequency of attrition, unanticipated events, and protocol violations. We will use quantitative measures compiled from screening, enrollment and study visit data entry logs. At regular study team meeting, comprehensive reports will include recruitment, retention and other performance parameters; quality control for data received; data that include missed visits and protocol violations, and participant characteristics. The organizational structure for the E-SNAP project is shown below:

MULTI-SITE RESEARCH

This is a single-site investigation at Northwestern University Institutional Review Board is the IRB of record for this study.

REFERENCES

Endeavor to Stop Nausea/Vomiting Associated with Pregnancy (E-SNAP) NCT05452174 09/30/2020

STATISTICAL DESIGN AND POWER ANALYSIS

Our data management team includes a highly experienced clinical trials statistician and database programmer. The REDCap management system was developed and functioning at Northwestern and is being transferred via a DUA. We are mindful of subjects' time and we send links to allow women to enter self-report measure data from home (for example, for recording of daily PUQE scores).

Analytic Approach. Descriptive statistics such as demographic and baseline clinical information will be summarized for all eligible women. These results will inform the feasibility, design and statistical approach for construction of the subsequent randomized controlled trial if the findings from the proposed study demonstrate the acceptability and feasibility of the protocol. This R21 study is not expected nor intended to have the power to address the outcomes described below, but to provide data to guide the design of a phase 3 RCT.

Aim 1. Define acceptability of mirtazapine for refractory NVP. Acceptability is defined by the number of women who accept participation compared to the total who undergo the consent procedure. All women will be asked for the reason behind their decision. A standard consort chart¹ will be created to record subject flow through the protocol. The acceptability of mirtazapine for NVP/HEG is a factor in the feasibility of the eventual RCT and is an important factor in the ability to recruit subjects and define the number of sites required.

Aim 2. Determine the tolerability and safety of the dosing regimen. Measures of tolerability include the proportions of: 1) emergent side effects on the ASE, which will be isolated by comparison to symptom ratings at intake; 2) withdrawals attributable to side effects; and 3) women who elect to continue mirtazapine after the initial 3-week trial. The daily PUQE scores will be used to evaluate the time (in days) to remission during the 3 week trial. We will use Kaplan-Meier curves to visualize time to remission (defined by a PUQE score of 3 or 4. Additionally, we will fit Cox regression models to identify factors that may be associated with time to remission.

We will evaluate the potential need for change in the dosing for the subsequent RCT by balancing the time to response against the emergence of any side effects. For example, if the 15 mg/day dose is well tolerated but the major symptom reduction occurs at 30 mg/day, we will consider the advisability of a more assertive dosing regimen with our DSMB and FDA consultants.

Aim 3. The drug tapering strategy will be assessed by evaluating the emergence of somatic symptoms on the Asberg side effects profile during the taper. Obtaining weekly plasma concentrations in the initial 21-day trial allows an exploration of whether a relationship between mirtazapine concentration and antinauseant/ antiemetic efficacy is likely in this group of women. The patient's genotypes and corresponding phenotypes (ultrarapid, rapid, intermediate, poor metabolizers--by specific enzyme) will be evaluated for their relationship to plasma mirtazapine concentrations. Biotransformation is mediated by CYP2D6, CYP3A4, and 1A2.²

Aim 4. Evaluate the maternal and fetal safety of mirtazapine. The maternal and neonatal outcomes from the PES will be reviewed for consistently reported events across subjects. We will compare the mirtazapine exposure data to that of women who have taken SSRI through pregnancy in our Obstetric-Fetal Pharmacology U54 study (N=88), Optimizing Medication Management for Mothers with Depression. Neonatologist [name] (see letter of support) will collaborate with our team to interpret the OPTI-MOM neonatal outcome data from the PES in the proposed trial (fetal exposure to mirtazapine) and compare it with the PES from our current OPTI-MOM subjects (fetal exposure to SSRI antidepressants). We have used these measures in our studies of SSRI exposure on neonates.³ The PES includes medical and obstetric risk factors, time in the delivery/ operating room, fetal monitoring, surgical complications, infant anthropometrics, special care/NICU admission, and post-birth complications. We will compare data using t-tests, chi-square test, and nonparametric tests as appropriate according to the type of data and their distributions.

Sample Size Considerations. The proposed study is not powered nor expected to evaluate the efficacy of mirtazapine for sNVP. To estimate a preliminary sample size for the efficacy of mirtazapine for NVP/HEG for the initial 3 week trial, we will assume 80% power, two-sided significance=.05, and a standard deviation of 2.1 (derived from Koren et al⁴), and a moderately severe PUQE score (\approx 10) at study entry. The standard deviation of the change in PUQE scores from baseline to week 3 is conservatively estimated to be 2.97 by assuming that the correlation is zero. With 20 subjects, we can detect a 23% reduction in mean symptom scores (a 2.3 point decrease in PUQE scores). Based on the case studies, we anticipate a more favorable symptom reduction than 2.3 points. To allow a 20%

dropout rate, we will enroll 25 subjects. We enrolled 2 participants, who completed the 3- week study at Northwestern, before the study was closed.

References.

- 1. Trials CTRo. The CONSORT Flow Diagram. Accessed.
